## SCHEMA

Advanced, recurrent or metastatic HNSCC  
Planned to receive immunotherapy (ICI)

ICI      RT      \*May receive up to 3 cycles of RT  
ICI cycle length = every 3 weeks

Blood and saliva collection for correlative analyses  
\*Collected if RT cycle given

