### 4.2 Study Design

This is a single-arm, non-randomized pilot study to evaluate the efficacy and tolerability of combination of **two standard of care interventions** (quad-shot palliative radiotherapy and pembrolizumab immunotherapy) for patients with advanced/recurrent/metastatic head and neck cancer.

Fifteen patients will be enrolled who have no curative localized treatment options, are eligible for palliative immunotherapy (pembrolizumab), have a lesion that can be targeted by radiotherapy, and are eligible for palliative radiotherapy as recommended by their radiation oncologist.

Quad-Shot Radiotherapy in Combination with Immune Checkpoint Inhibition for  
Advanced/Recurrent Head and Neck Cancer  
Wake Forest Baptist Comprehensive Cancer Center  
WFBCCC60320

Patients eligible for this study will be those scheduled to receive palliative immunotherapy with the immune checkpoint inhibitor pembrolizumab (which is standard of care) for advanced, R/M head and neck SCC according to standard of care practice. They will also be eligible for palliative quad-shot radiotherapy according to the standard of care for advanced/recurrent/metastatic HSNCC. Quad-shot radiotherapy will be applied between immunotherapy cycle 2-3 or between immunotherapy cycle 3-4, within the last week of the cycle, and not to be delivered on the same day as ICI administration. Up to two additional quad-shot cycles will be delivered between cycles 6-7 or 7-8 (prior to cycle 8) and 11-12 or 12-13 (prior to cycle 13) of immunotherapy. The additional quad-shot treatments will be delivered in a similar fashion, in the last week of the ICI cycle.

Restaging imaging with CT, MRI or PET/CT will be obtained every 5-6 immunotherapy treatments. For the purposes of lesion measurements, follow-up imaging must be performed using the same modality (CT or MRI) as was used for initial baseline imaging. PET/CT may be utilized for follow-up imaging at the clinician's discretion. The maximum response in the targeted lesion and in the non-targeted lesions will be assessed. Subsequent immunotherapy cycles will be delivered after quad-shot radiotherapy until tumor progression or treatment intolerance.

Palliative local (non-systemic) interventions to other sites that are not quad-shot radiotherapy target sites is allowable while on study protocol treatment for the management of cancer symptoms. This should not be utilized for progression of disease at that site.

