- c. With first administration of pembrolizumab only and then as clinically indicated. Subjects will have their blood pressure and pulse measured before, during and after the infusion at the following times (based on a 60-minute infusion):
  - At the beginning of the infusion (at 0 minutes)
  - At 30 minutes during the infusion ( $\pm 5$  minutes)
  - At the end of the infusion (at 60 minutes  $\pm 5$  minutes)
  - In the 1 hour observation period post-infusion: 30 and 60 minutes after the infusion (ie, 90 and 120 minutes from the start of the infusion) ( $\pm 5$  minutes) – for the first infusion only and then for subsequent infusions as clinically indicated
  - If the infusion takes longer than 60 minutes then blood pressure and pulse measurements should be collected every 30 minutes ( $\pm 5$  minutes) and as described above or more frequently if clinically indicated.
- d. ECG during screening and at Day1 –baseline. Thereafter as clinically indicated. Baseline and abnormal ECG at any time in triplicate others single. Triplicate EKG is only needed at screening, and not on Cycle 1 Day 1 unless something clinically significant was seen at screening.
- e. Free T3 and free T4 will only be measured if TSH is abnormal. They should also be measured if there is clinical suspicion of an adverse event related to the endocrine system.
- f. CT (preferred) or MRI scans, preferably with IV contrast, are collected during screening (for baseline) and as close to and prior to initiation of study treatment but not more than 14 days  $\pm$  5 days prior to first treatment. Will then be performed every 5 cycles ( $\pm$  1 cycle) for tumor response measurement
- g. PET scan will be performed in all cases if reimbursed by Medical Insurance or funded. It will be performed as close to the initiation of treatment but not more than 28 days prior to treatment. Will then be performed in follow up as clinically indicated and if approved by medical insurance.

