## **7.0 Measurement of Effect**

### **7.1 Antitumor Effect – Solid Tumors**

In accordance with the standard of care, after a baseline scans obtained prior to study registration, patients will be reevaluated for response after 5 cycles of immunotherapy. Patients who continue to receive ICI at the discretion of the medical oncologist will be evaluated again after 10 cycles of ICI.

Response and progression will be evaluated in this study using the Response Evaluation Criteria in Solid Tumors (RECIST) criteria 1.1.(40) Changes in the largest diameter

(unidimensional measurement) of the tumor lesions and the shortest diameter in the case of malignant lymph nodes are used in the RECIST criteria.

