#### 7.1.5 Survival Outcomes

Progression-Free Survival is defined as the duration of time from registration to the time of progression, death, or date of last contact; those lost to follow-up will be censored.

Overall Survival is defined as the duration of time from registration to date of death or date of last contact; those lost to follow-up will be censored.

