### **Severe and Fatal Immune-Mediated Adverse Reactions**

Immune-mediated adverse reactions, which may be severe or fatal, can occur in any organ system or tissue and usually occur during treatment; however, they can also occur after discontinuation. Early identification and management are essential to ensuring safe use of PD-1-blocking antibodies. Monitor for symptoms and signs of immune-mediated adverse reactions. Evaluate clinical chemistries, including liver tests and thyroid function tests, at baseline and periodically during treatment. Institute medical management promptly to include specialty consultation as appropriate.

In general, withhold pembrolizumab for Grade 3 or 4 and certain Grade 2 immune-mediated adverse reactions. Permanently discontinue pembrolizumab for Grade 4 and certain Grade 3 immune-mediated adverse reactions. For Grade 3 or 4 and certain Grade 2 immune-mediated adverse reactions, administer corticosteroids (1 to 2 mg/kg/day prednisone or equivalent) or other appropriate therapy until improvement to Grade 1 or less followed by a corticosteroid taper over 1 month. Consider administration of other systemic immunosuppressants in patients whose immune-mediated adverse reaction is not controlled with corticosteroids. Institute hormone replacement therapy for endocrinopathies as warranted.

**Immune-mediated pneumonitis:** Immune-mediated pneumonitis occurred in about 2.5% of the patients treated with immune checkpoint inhibitors and leads to permanent discontinuation of the drug in about half of the patients. Systemic corticosteroids are required in all patients with pneumonitis. Withhold pembrolizumab for Grade 2, and permanently discontinue for Grade 3 or 4. Resume in patients with complete or partial resolution (Grade 0 to 1) after corticosteroid taper.

**Immune-mediated colitis:** Immune-mediated colitis occur in about 1% of patients receiving immune checkpoint inhibitors leading to permanent discontinuation pembrolizumab in a small percent of patients. Systemic corticosteroids are required in all patients with colitis. Withhold pembrolizumab for Grade 2 or 3, and permanently discontinue for Grade 4. Resume in patients with complete or partial resolution (Grade 0 to 1) after corticosteroid taper.

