### 11.2 Analysis of Secondary Objective

There are 6 secondary outcomes of interest for this pilot study. These are 1) response rate for the target lesion; 2) response rate for non-target lesions 3) duration of response for the target lesion 4) progression free survival (PFS) 5) overall survival (OS) and tolerability assessed using PRO-CTCAE. We now describe our analytic approach for each measure.

For the response rate measures we will estimate the percent of responders (PR or CR) and the corresponding 95% Clopper Pearson exact confidence intervals. For the duration of response, among responders we will estimate both the mean and median duration and the corresponding 95% confidence intervals for the mean and inter-quartile range for the median. For time to event measures (PFS and OS) we will estimate Kaplan Meier survival curves and estimate the median time to event times as well as the percent PFS and OS at 6 months and 1 year post treatment. For tolerability, we will estimate the percent of patients with different AEs assessed using the PRO-CTCAE and corresponding 95% Clopper Pearson exact confidence intervals.

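### The 6-month and 1-year PFS landmarks normally fall between planned scans, so Kaplan-Meier PFS at 6 months is likely overstated; report PFS just after a scan window closes

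*Combined protocol and SAP*

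**What the plan says.** Section 11.2 plans Kaplan-Meier curves for PFS and OS and will "estimate the median time to event times as well as the percent PFS and OS at 6 months and 1 year post treatment". Section 7.1.5 sets the clock: "Progression-Free Survival is defined as the duration of time from registration to the time of progression, death, or date of last contact".

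Scan timing is given in three places, each time as a count of infusions:

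- Section 4.2: "Restaging imaging with CT, MRI or PET/CT will be obtained every 5-6 immunotherapy treatments".
- Section 6.1, footnote f: "Will then be performed every 5 cycles", with a window of plus or minus one cycle.
- Section 7.1: "patients will be reevaluated for response after 5 cycles of immunotherapy", and again after 10 cycles for those who continue.

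The Schema fixes the unit: "ICI cycle length = every 3 weeks". After treatment ends, section 6.5 leaves tumor imaging to the treating physician.

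No section says how a progression date is assigned when a scan finds it, names a method for interval-censored data, or ties a PFS landmark to a scan.

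**The concern.** A scan shows that progression has happened, not when. Unless the plan says otherwise, the event is dated at the scan that finds it. A landmark early in the gap after a scan loses little. A landmark late in the gap loses nearly all the scan-detected progression since the last scan. Six months is about week 26, late in the gap between weeks 15 and 30.

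On the nominal schedule the error runs one way. Sections 11.1 and 11.3 plan estimates and no test, so the estimates are what the pilot delivers, and 6-month PFS is one of the named ones. A reader who compares it with a study scanned on another schedule would credit the combination with control that comes partly from the calendar.

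**Working it through.** **The plan's own figure.** The only design figure is in section 11.3: a maximum 95% Clopper-Pearson width of 0.52 with 15 patients. At 7/15 the exact interval is 0.213 to 0.734, width 0.521, so it reproduces. It gives the scale of sampling error. One patient in 15 is 6.7 points.

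**Scan weeks** = 3 × number of cycles.

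- Every 5 cycles (nominal): weeks 15, 30, 45, 60.
- Window of ±1 cycle around those fixed points: 12–18, 27–33, 42–48, 57–63.
- Section 4.2, every 5–6 treatments: 15–18, 30–36, 45–54.
- Every interval 4 cycles, if footnote f allows it: 12, 24, 36, 48.
- Every interval 6 cycles: 18, 36, 54.

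Six months is week 26.1 and one year is week 52.2. On the nominal schedule week 26 is 11 weeks after scan 1 and 4 weeks before scan 2; week 52 lies between weeks 45 and 60. With the window anchored to the nominal cycles, scan 2 is at week 27 at the earliest.

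**Model (assumption).** The documents state no PFS rate or median, so take S(t) = exp(−λt), λ = ln 2 / median, with medians of 2 to 12 months. Let a share f of events (deaths, clinically found progression) be dated when they occur and the rest at the next scan. Then

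reported PFS at week 26.1 = exp(−(1−f)·λ·15 − f·λ·26.1).

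Example, median 4 months: λ = 0.693 / (4 × 4.348) = 0.0399 per week. True S(26.1) = 35.4%. With f = 0, reported = S(15) = 55.0%, an excess of 19.6 points. With f = 0.5, reported = 44.1%, an excess of 8.7 points.

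| Assumed median (months) | True 6-month PFS | Reported, f = 0 | Excess, f = 0 | Excess, f = 0.25 | Excess, f = 0.5 | 1-year excess, f = 0 |
|---|---|---|---|---|---|---|
| 2 | 12.5% | 30.3% | 17.8 | 11.8 | 6.9 | 1.2 |
| 3 | 25.0% | 45.1% | 20.1 | 13.9 | 8.6 | 2.9 |
| 4 | 35.4% | 55.0% | 19.6 | 13.9 | 8.7 | 4.1 |
| 6 | 50.0% | 67.1% | 17.1 | 12.4 | 7.9 | 5.3 |
| 9 | 63.0% | 76.7% | 13.7 | 10.0 | 6.5 | 5.4 |
| 12 | 70.7% | 81.9% | 11.2 | 8.3 | 5.4 | 5.0 |

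A simulation with scans moved at random by −1, 0 or +1 cycle gives 9 to 10 points at f = 0.5 for medians of 3 to 5.7 months; hence the range of about 5 to 10.

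**Sensitivity to the schedule** (f = 0, medians 4 to 6 months).

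- All intervals 4 cycles: scan 2 is at week 24 and the 6-month excess is about 3 points.
- All intervals 6 cycles: 12 to 14 points at 6 months. At 1 year the last scan is at week 36, and the excess is 11 to 13 points.
- Clock from registration, with 1 to 2 weeks to first dose and 5-cycle spacing: 14 to 18 points at 6 months.

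**Effect of moving the landmark** (nominal scans, f = 0, median 4 months). At week 33 the excess is S(30) − S(33) = 30.3 − 26.8 = 3.4 points, against 19.6 at week 26. At week 48 it is S(45) − S(48) = 16.6 − 14.8 = 1.9 points, against 4.1 at week 52.

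**The case against.** The best reply is that this is a secondary, descriptive endpoint with 15 patients, no test and no PFS benchmark, and that a binomial interval at this size may be 52 points wide. That limits the weight of the point. It does not remove it: a wide interval shows sampling error, not a shift built into the scan calendar.

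Four stronger readings are tempting, and the documents do not support them.

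- *That 6-month PFS is essentially the week-15 status.* Deaths count when they occur (7.1.5). Clinical and pathologic findings can document progression under 7.1.4, although that text concerns duration of response. Superficial lesions may be measured by calipers (7.1.2). The reading holds only if most progression is found by scheduled scan.
- *That treatment holds inflate 6-month PFS further.* Section 8.1 has corticosteroids until recovery, "followed by a corticosteroid taper over 1 month", and the scan grid counts infusions. But on the nominal schedule a 4-week hold before scan 1 moves it from week 15 to week 19, nearer to week 26. At a 4-month median the reported figure falls from S(15) = 55% to S(19) = 47%. A hold between scans 1 and 2 changes nothing at week 26, because scan 2 is already later. Only a hold of more than 11 weeks before scan 1 would push that scan past week 26.
- *That PFS is a stated planning result.* Section 11.1 says that of the overall response rate, and the threshold in 11.3 for further study is also a response rate.
- *That an interval-censored estimate at 6 months is the remedy.* If patients are scanned near weeks 15 and 30, Turnbull's estimator does not determine S(26) within that interval. A Weibull fit fills the gap with a shape assumption on 15 patients.

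Two further objections stand in part. The size depends on the reading of footnote f: if each interval may be 4 cycles, little bias remains. And the comparison with week 26 takes the clock to start near first dose, whereas 7.1.5 starts at registration and 11.2 counts its landmarks after treatment. If that means after treatment ends, imaging is discretionary and the infusion grid no longer governs.

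**Conclusion.** The point holds. On the nominal schedule both PFS landmarks fall between scans, and plain Kaplan-Meier with progression dated at the scan biases 6-month PFS upward. The excess is about 11 to 20 points (roughly two to three patients in 15) if all progression is scan-detected, and about 5 to 10 points (roughly one patient) if half of events are dated when they occur. At 1 year it is about 1 to 5 points nominally, and 11 to 13 with 6-cycle spacing.

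These sizes rest on an assumed exponential curve with a median of 2 to 12 months, a clock that starts near first dose, and 5-cycle spacing unless stated. The direction on the nominal schedule does not depend on the curve. The weight is modest: the remedy is cheap, the endpoint is secondary and descriptive, and nothing in the primary analysis or in OS is affected.

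**What to change.** 1. In 11.2 and 7.1.5, state one PFS time origin, and state that progression found by scan is dated at that scan.
2. Reconcile the scan schedules in 4.2, 6.1 footnote f and 7.1. Say whether the one-cycle window is anchored to cycles 5, 10 and 15 or applies to each interval. If consecutive 4-cycle intervals are allowed, week 33 would lie 9 weeks after a week-24 scan and would not serve.
3. In 11.2, report PFS just after a scheduled scan window closes: about weeks 33 and 48 under footnote f with an anchored window, or weeks 36 and 54 under 4.2. These weeks count from first pembrolizumab. If the origin stays at registration, add the allowed time to first dose.
4. If 6- and 12-month PFS are kept for comparison with other studies, label them as dependent on the scan schedule and likely overstated.
5. Leave OS at 6 and 12 months.

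The cost is wording in the protocol and no added scans. The landmarks are less conventional and the PFS figure will be slightly less favourable. On the model above (4-month median, all progression scan-detected), moving from week 26 to week 33 cuts the excess from about 20 points to about 3. Under the 4.2 schedule at week 36, a patient scanned at week 30 still carries S(30) − S(36) = 30.3 − 23.8 = 6.4 points, and one scanned at week 36 carries none.

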### 2.1 Primary Objective(s)

2.1.1 Measure the overall response rate for immunotherapy given with quad-shot radiotherapy

### 2.2 Secondary Objective(s)

2.2.1 Measure the response rate at the target lesion.

Quad-Shot Radiotherapy in Combination with Immune Checkpoint Inhibition for  
Advanced/Recurrent Head and Neck Cancer  
Wake Forest Baptist Comprehensive Cancer Center  
WFBCCC60320

- 2.2.2 Measure the response rate at non-target sites *in patients with non-target sites.*
- 2.2.3 Evaluate the durability of response at the target lesion.
- 2.2.4 Evaluate progression-free survival.
- 2.2.5 Evaluate overall survival.
- 2.2.6 Assess the tolerability of the combination of quad-shot radiotherapy with immunotherapy in order to assess the feasibility of this treatment regimen.

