The study treatment portion ends for all patients with the last administration of the immunotherapy.

We will monitor and document clinical toxicity per NCI Common Terminology Criteria for Adverse Events version 5.0 during the treatment and for two additional visits 30 days apart from the end of treatment with immunotherapy. Subjects who decline to return to the site for evaluations will be offered follow-up by phone up to 2 months as an alternative and the PI will make every effort to collect toxicity data from medical records.

Patients will be subsequently followed for progression-free survival and overall survival outcomes. Subsequent visits can be accomplished in person or over the phone and clinical and imaging data will be collected from medical records as available.

Patient-reported outcomes will be obtained at each time point using a tailored checklist of PRO-CTCAE head and neck cancer-specific items.

Saliva and blood for correlative studies will be collected before each treatment with immunotherapy for the first 5 administrations and before the quad-shot administration. Saliva and blood samples will only need to be collected on the first day of Quadshot treatment. In the cases in which the patients will receive a 2nd quad-shot and possibly a third quad-shot, blood and saliva will be collected before the respective radiation treatments as well as before the immunotherapy cycles that proceed and follow the quad-shot treatments.

PD-L1 receptors will be tested in all patients as per standard of care. Next generation sequencing is encouraged and will be done whenever possible from the blood or tumor if available.

Quad-Shot Radiotherapy in Combination with Immune Checkpoint Inhibition for  
Advanced/Recurrent Head and Neck Cancer  
Wake Forest Baptist Comprehensive Cancer Center  
WFBCCC60320

If any patient does not complete the study treatment and investigations, the patient will be replaced.

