#### **5.2 Secondary Outcomes**

- 5.2.1 The response rate in the target lesion measured according to RECIST 1.1 (Section 7.1.3).
- 5.2.2 The response rate in the non-target lesions (if applicable) will be measured according to RECIST 1.1 (Section 7.1.3).
- 5.2.3 The duration of response at the target lesion will be defined as the duration from the time measurement criteria are met for CR or PR (whichever is first recorded) until the first date of recurrent or progressive disease as defined in Section 7.1.4.

Quad-Shot Radiotherapy in Combination with Immune Checkpoint Inhibition for  
Advanced/Recurrent Head and Neck Cancer  
Wake Forest Baptist Comprehensive Cancer Center  
WFBCCC60320

- 5.2.4 Progression-free survival (PFS) will be defined as in Section 7.1.5.
- 5.2.5 Overall survival (OS) will be defined as in Section 7.1.5.
- 5.2.6 Tolerability will be measured using the Patient-Reported Outcomes version of the Common Terminology Criteria for Adverse Events (PRO-CTCAE).

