## 6.0 Treatment Plan

### 6.1 Study Calendar

	Screening/ Pre- Registration i	Cycle 1-3 ICI	QuadShot #1	Cycles 4-6 ICI	QuadShot #2	Cycles 7-11 ICI	Quadshot #3	Maintenance ICI Every 3 Weeks
Initial Screening for Eligibility	X							
Informed Consent	X							
Demographics	X							
Medical and Surgical History	X							
Medication List	X							
Comorbidities	X							
Tobacco Use History	X							
Pre-Toxicity Form	X							
Hepatitis A antibody Hepatitis B surface Ag, Hepatitis C antibody and HIV	X							
Urine hCG or serum $\beta$ hCG a	X	As clinically indicated						
Pembrolizumab Administration		X		X		X		X
Quad-shot Radiotherapy h			X		X		X	
Physical Examination b	X	X		X		X		X
Vital Signs	X	X c		X		X		X

Quad-Shot Radiotherapy in Combination with Immune Checkpoint Inhibition for Advanced/Recurrent Head and Neck Cancer  
 Wake Forest Baptist Comprehensive Cancer Center  
 WFBCCC60320

Electrocardiogram d	X	X	As clinically indicated				
Concomitant Medications	X	X		X		X	
Adverse event/serious adverse event assessment				X		X	
ECOG Performance Status	X	X	X m	X	X m		X m
Liver enzyme panel	X	X i		X		X	X
Serum Chemistry	X	X i		X		X	X
Magnesium	X		As clinically indicated				
Uric Acid	X		As clinically indicated				
LDH	X	X i	As clinically indicated				
Amylase, Lipase	X	X i		X		X	X
Thyroid function tests (TSH and fT3 and fT4) e	X	X i		X		X	X
Hematology	X	X i		X		X	X
Urinalysis	X		As clinically indicated				
Coagulation parameters	X		As clinically indicated				
Tumor Assessment with CT scan or MRI f	X		X		X		X
Tumor assessment with PET scan g	X		X		X		X
Blood Collection for Correlatives		X	X	X k	X k	X k	X k
Saliva Collection for Correlatives		X	X	X k	X k	X k	X k
PRO-CTCAE QOL Questionnaire h		X		X		X	X

Quad-Shot Radiotherapy in Combination with Immune Checkpoint Inhibition for Advanced/Recurrent Head and Neck Cancer  
Wake Forest Baptist Comprehensive Cancer Center  
WFBCCC60320

- a. Female subjects of childbearing potential only
- b. Full physical examination at baseline; targeted physical examination at other timepoints

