### 7.1.1 Definitions

- **Evaluable for toxicity:**

Only those patients who have received at least 1 fraction of radiotherapy and at least 1 cycle of ICI will be evaluable for toxicity from the time of their first fraction of radiotherapy.

- **Evaluable for objective response:**

Only those patients who received at least one cycle of quad-shot radiotherapy (given after at least 2 cycles of ICI), and have had their target disease re-evaluated will be evaluable. These patients will have their response classified according to the definitions stated below.

Note: Per Section 6.6, subjects who are removed from study prior to completing at least 2 cycles of ICI followed by at least 1 cycle of quad-shot radiotherapy followed by at least 2 cycles of ICI will be discontinued from the study and replaced.

- **Evaluable Non-Target Disease Response.**

Patients who have lesions present at baseline that are evaluable but do not meet the definitions of target disease, have received at least one cycle of quad-shot radiotherapy, and have had their disease re-evaluated will be considered evaluable for non-target disease. The response assessment is based on the presence, absence, or unequivocal progression of the lesions.

- **Measurable disease / measurable lesions**

Measurable lesions are defined as those that can be accurately measured in at least one dimension (longest diameter to be recorded) as  $\geq 20$  mm by chest x-ray, as  $\geq 10$  mm with CT scan, or  $\geq 10$  mm with calipers by clinical exam. All tumor measurements must be recorded in millimeters (or decimal fractions of centimeters).

- **Malignant lymph nodes.**

To be considered pathologically enlarged and measurable, a lymph node must be  $\geq 15$  mm in short axis when assessed by CT scan (CT scan slice thickness recommended to be no greater than 5 mm). At baseline and in follow-up, only the short axis will be measured and followed.

- **Non-measurable disease / non-measurable lesions:**

All other lesions (or sites of disease), including small lesions (longest diameter  $<10$  mm or pathological lymph nodes with  $\geq 10$  to  $<15$  mm short axis), are considered non-measurable disease. Bone lesions, leptomeningeal disease, ascites, pleural/pericardial effusions, lymphangitis cutis/pneumonitis, inflammatory breast disease, and abdominal masses (not followed by CT or MRI), are considered as non-measurable.

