### 8.1 Safety Parameters

#### **Definition of adverse events:**

The International Conference on Harmonization (ICH) Guideline for Good Clinical Practice (GCP) E6(R1) defines an AE as:

Any untoward medical occurrence in a patient or clinical investigation subject administered a pharmaceutical product and which does not necessarily have a causal relationship with this treatment. An AE can therefore be any unfavorable and unintended sign (including an abnormal laboratory finding), symptom, or disease temporally associated with the use of a medicinal product, whether or not considered related to the medicinal product.

An AE includes but is not limited to any clinically significant worsening of a subject's pre-existing condition. An abnormal laboratory finding (including ECG finding) that requires an action or intervention by the investigator, or a finding judged by the investigator to represent a change beyond the range of normal physiologic fluctuation, should be reported as an AE.

Adverse events may be treatment emergent (ie, occurring after initial receipt of investigational product) or nontreatment emergent. A nontreatment-emergent AE is any new sign or symptom, disease, or other untoward medical event that begins after written informed consent has been obtained but before the subject has received investigational product.

Elective treatment or surgery or preplanned treatment or surgery (that was scheduled prior to the subject being enrolled into the study) for a documented pre-existing condition, that did not worsen from baseline, is not considered an AE (serious or nonserious). An untoward medical event occurring during the prescheduled elective procedure or routinely scheduled treatment should be recorded as an AE or SAE.

The term AE is used to include both serious and non-serious AEs.

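### The tolerability percentage in Section 11.2 makes no use of a baseline PRO-CTCAE score, so an unchanged pre-existing symptom counts as an adverse event

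*Combined protocol and SAP*

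**What the plan says.** Objective 2.2.6 is to "Assess the tolerability of the combination of quad-shot radiotherapy with immunotherapy in order to assess the feasibility of this treatment regimen". Section 5.2.6 names PRO-CTCAE as the measure. The whole planned analysis is the sentence in Section 11.2: "For tolerability, we will estimate the percent of patients with different AEs assessed using the PRO-CTCAE", with exact 95% intervals. No baseline, worsening rule, score threshold or time window is given.

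Other sections bear on the point without settling it:

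- Section 4.2: "Patient-reported outcomes will be obtained at each time point using a tailored checklist of PRO-CTCAE head and neck cancer-specific items".
- Section 6.1: the row "PRO-CTCAE QOL Questionnaire" has no mark at screening. Its first mark is under ICI Cycles 1-3. A "Pre-Toxicity Form" is marked at screening, but no analysis uses it.
- Section 7.1.1: patients who have had at least one radiotherapy fraction and one ICI cycle "will be evaluable for toxicity from the time of their first fraction of radiotherapy".
- Section 8.1: "An AE includes but is not limited to any clinically significant worsening of a subject's pre-existing condition".
- Section 6.2: adverse events are assessed at Months 1 and 2 after treatment. PRO-CTCAE is not listed there.

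**The concern.** Patients are likely to have symptoms at entry. They have incurable head and neck cancer with a site for which palliative radiotherapy is recommended (3.1.2). Recurrence within irradiated tissue is allowed (3.1.1.2). The toxicity exclusion in 3.2.10 applies only above grade 2 and exempts some irreversible effects. The questionnaire is a head and neck checklist, so it asks about symptoms that the tumor and earlier treatment can cause.

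The trial has one arm, so the patient's own earlier score is the only available comparator. Without it, a high percentage could reflect disease, earlier treatment or the study regimen, and relief of a symptom cannot show. This is the only analysis that Section 11.2 plans for the tolerability and feasibility objective.

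**Working it through.** **1. The plan's own precision figure.** The Clopper-Pearson limits are Beta(0.025; x, n-x+1) and Beta(0.975; x+1, n-x). With n = 15 and x = 7 they are 0.2127 and 0.7341, a width of 0.52. This reproduces the maximum width stated in Section 11.3 and is not in dispute. The documents give no tolerability rate to reproduce.

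**2. What the raw percentage contains.** Let b be the share with the symptom at baseline, s the share of those in whom it persists, and q the share of the others who develop it. Then:

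- raw percentage = b·s + (1-b)·q
- new-onset percentage = (1-b)·q
- difference = b·s

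The difference cannot be negative. Its size depends on b and s, which the documents do not give. With q = 0.20 assumed:

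| b | s | Raw | New onset |
|---|---|---|---|
| 0.2 | 1 | 0.2 + 0.8×0.2 = 36% | 16% |
| 0.4 | 1 | 0.4 + 0.6×0.2 = 52% | 12% |
| 0.6 | 1 | 0.6 + 0.4×0.2 = 68% | 8% |
| 0.8 | 1 | 0.8 + 0.2×0.2 = 84% | 4% |
| 0.4 | 0.5 | 0.2 + 0.6×0.2 = 32% | 12% |
| 0.6 | 0.5 | 0.3 + 0.4×0.2 = 38% | 8% |

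With no treatment effect (q = 0), b = 0.6 and s = 1, 15 patients would give 9/15 = 60% (95% CI 32% to 84%) raw, against 0/15 (0% to 22%) new onset.

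**3. How worsening from baseline behaves.** A score that fluctuates will sometimes exceed its baseline by chance, more so when the worst of several visits is compared with one baseline. To size this, take patient i at visit j = 0 (baseline) to 5 with latent value z = √ρ·u(i) + √(1-ρ)·e(i,j), where u and e are standard normal. There is no treatment effect. Cut-points put 40% of patients at score 1 or above, and those patients are split 40/30/20/10 over scores 1 to 4. Prevalence, ρ, number of visits, scale and split are all assumptions.

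| ρ | Any report over 5 visits (raw) | Worst later score above baseline | Score above baseline at one fixed visit |
|---|---|---|---|
| 0.95 | 50% | 27% | 12% |
| 0.8 | 61% | 43% | 19% |
| 0.6 | 71% | 54% | 23% |

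The raw percentage at one fixed visit is 40% throughout. Other severity splits move the worsening figures by a few points. Using the baseline lowers the false signal but does not remove it. The fixed-visit comparison is the least inflated of the three.

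**4. Whether another section closes the gap.** Section 7.1.1 sets when toxicity evaluation begins, and a symptom present before and after that date is still counted. The wording on worsening in Section 8.1 belongs to safety reporting and is not linked to PRO-CTCAE scores. The screening form has no stated analytic use.

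**The case against.** The strongest reply is that Section 11.2 is silent and does not lay down a rule. It speaks of adverse events, a term the protocol defines to include worsening of a pre-existing condition, and the protocol sets a start for the toxicity window and collects a screening toxicity form. A reader might infer that the plan expressly treats baseline symptoms as treatment toxicity, or discards the baseline on purpose. The documents do not say that. What remains is that none of these elements is tied to PRO-CTCAE scoring, so the sentence applied literally counts unchanged symptoms.

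Four further points stand in part:

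- **Size.** Prevalence, correlation, visit count and the ever-reported window are all assumed. It is tempting to set the raw 50-71% against the 11-33% with binary new onset (no symptom at baseline, symptom later) in the same model. That is not the worsening measure recommended here and would overstate the gain.
- **Follow-up.** A reader might see a contradiction between 4.2 and 6.2. The phrase on time points in 4.2 is undefined and can mean treatment visits, and follow-up may be by phone or from records. The calendar footnote on PRO-CTCAE is incomplete in the text as read, so nothing is argued from it.
- **Timing.** That the Cycle 1 form precedes the first dose is an inference; the calendar does not say so.
- **Consequence.** This is one of six secondary outcomes in an estimation-only pilot with no tolerability threshold. Clinician-graded CTCAE toxicity is also collected, so PRO-CTCAE is not the only toxicity information, although 11.2 plans no analysis of the CTCAE data. PRO-CTCAE forms are kept (13.2), so change could be computed later, but then the choice of measure would follow sight of the data.

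**Conclusion.** The concern holds as a gap in the specified estimator. As written, the percentage includes every patient whose earlier symptom persists, and in a single-arm trial it cannot be read as an effect of the combination. The direction follows from the algebra: the raw figure exceeds new onset by b·s. The size is not known. Under the stated assumptions and no treatment effect, the raw figure over five visits is 50-71%, against about 27-54% for worst score above baseline and 12-23% at a fixed visit. These are illustrations only. The primary endpoint, the sample size and the stated interval width are unaffected, so this is a change worth making before the data are analyzed rather than a threat to the trial.

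**What to change.** - **Section 6.1:** state that the Cycle 1 PRO-CTCAE is completed before the first pembrolizumab dose.
- **Section 11.2, baselines:** name that form as the baseline, and the last form before quad-shot #1 as a second baseline for the radiotherapy period.
- **Section 11.2, estimates:** beside the raw percentage, report for each item the percentage of patients whose score worsens from baseline by a pre-set threshold within a pre-set window, with Clopper-Pearson intervals. Because a maximum over visits rises by chance, also report worsening at fixed visits.
- **Sections 4.2 and 6.2:** clarify whether the PRO time points include Months 1 and 2. Adding the questionnaire at those visits is optional.

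The core change uses forms already scheduled and needs only protocol and analysis wording. The cost is a little more analysis. Intervals stay wide at 15 patients, as Section 11.3 already accepts. The optional follow-up forms would add slightly to patient burden.
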